#### 4.1.4 Missing data

#### 4.1.4.1 General considerations

(ICH E3; 9.7.1, 11.4.2.2. ICH E9; 5.3. EMA Guideline on Missing Data in Confirmatory Clinical Trials) Missing data will be imputed for five main endpoints of this study (UNS, PDSS, UNS-CTP, WRC and MWT). For the other endpoints no missing value will be imputed.

A Multiple Imputation (MI) procedure will be used to impute the missing evaluations, as a prior step, assuming that those patients would be in their randomized arm. The partially complete datasets will be generated with a model including the following covariates age, gender and the main model components (section 2.2).

A total of 100 imputed partially complete datasets will be generated.

MI inference involves 3 consecutives phases:

- 1/ Imputation step:

The missing pattern is supposed to be monotone, so the regression method will be used to impute missing data.

The partially complete datasets will be generated with a model including age, gender factors and taking into account the baseline score of the primary endpoint, based on patient which every postbaseline measurement available. It is of note that this imputation step might be preceded by one MI approach based on MCMC method, in case of arbitrary missing pattern. A total of 100 imputed partially-complete datasets will be generated.

The mean MD imputation will based on Missing at Random (MAR) corresponding to the hypothesis that missingness is assumed independent of the outcome, or to estimate a "de jure" (per protocol) estimand, censoring after any protocol deviation. This hypothesis was considered as the most likely in this particular context.

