Despite the likelihood of this option, a secondary MD imputation will be conducted according to the Missing at Random hypothesis (MNAR), for which several options to construct the joint distribution of the observed and unobserved data have been proposed, each reflecting a different MNAR mechanism (Carpenter et al., 2013). This appropriate choice was discussed in the general context of narcolepsy. We assumed that after dropping out, participants from the active arm have the same outcomes as the reference group individuals, hypothesizing that the treatment effect is lost after the individual leaves the study. This option is called Jump to reference (J2R), after dropout, the participant's conditional outcomes are associated to those of the control arm. The joint distribution is a Multivariate Normal model with mean parameters from the randomised arm until date of interruption (Di) and from the reference group afterward. The covariance matrix corresponds to the parameters from the randomised arm until Di and to the reference group for the conditional components of the post-dropout variables, given the pre-dropout measurements.

Concerning the J2R, the jump-to-placebo approach will be set up for these patients' imputations, by using the %mistep macro from James Roger (https://www.lshtm.ac.uk/research/centres-projects-groups/missing-data#dia-missing-data, zip file MISTEP20180327).

Usualy, a sequence of %mistep is run, the subsequent models include the residuals of the previous model. In this study only one model will be used (for the endpoint value imputation).

In case of imputed data outside the range, the minimun or the maximun bound will be used.

This macro will be used because no SAS procedure are currently available to perform the jump to reference approach.

- 2/ Analysis step:

The same analysis as described above will be applied to each of the 100 imputed datasets.

- 3/Combination step:

Statistical inferences will be generated by combining results from 100 analyses using Rubin's formulae (Rubin, 1987).

The multiple imputation estimator of the difference between active treatment and placebo is the average of the individual 100 estimators. The variance of the estimator is the combination of the between and within-imputation variability (Kenward & Carpenter, 2007).

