## Analysis:

A negative Binomial Regression will be used according to the general model (section 2.2) for WRC estimated during the period V6-V7 (Justification Plazzi 2021) only in the type I Narcolepy patients (for other patients we don't have the baseline value). The WRC at baseline will be used as a fixed covariate and center as random (In case of non convergence of the model, this one can be updated).

The same way as the primary analysis (Including sensitivity analyses) will be performed: MAR and MNAR imputation and observed cases.

In addition,

- Descriptive statistics by treatment group during the following intervals: Baseline (D-28 to D0),
   Final DB last 6 weeks DB4=D21-D63 (i.e. V4-V7), Final DB last 2 weeks: DB2=D49-D63 (i.e. V6-V7) will be provided
- A supportive analysis will be to compare the proportion of patients such that WRC <1 between treatment groups (simple logistic regression providing OR with 95%CI)

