## Analysis:

MWT was right censored after 30 minutes, resulting into a truncated asymmetric distribution (Plazzi 2021).

A Cox proportional regression will be conducted in considering time to sleep onset (mean of the 4 tests at final visit) and survival response defined as non-response (0=patient remained awake until 30 minutes) and response (1=patient falling asleep before 30 minutes). Patients early terminating for treatment-related or -unrelated reason will be considered as responders or right-censored at the time of interruption, respectively. Center will be considered as a cluster variable in the Cox model to allow calculation of robust variance for the model assuming clusters with correlated observations [Andersen 1982, Therneau 2000].

This analysis will be done only in patients with at least a baseline value or a final value (V7 or the last on-study visit).

The same way as the primary analysis (Including sensitivity analyses) will be performed: MAR and MNAR imputation, center as fixed effect (in MAR imputation) and observed cases.

Descriptive statistics (mean values for each latency parameter and number of Sleep onset in SP) at baseline and V7 by treatment group will be provided.

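### Weekly cataplexy rate is imputed by a generic, in effect normal, regression but analysed as a negative binomial count; the resulting bias depends on dispersion and on missingness by arm

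*SAP*

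**What the plan says.** SAP 4.1.4.1 lists the endpoints that share one imputation scheme: "Missing data will be imputed for five main endpoints of this study (UNS, PDSS, UNS-CTP, WRC and MWT"). For the main missing-at-random (MAR) step it says "so the regression method will be used to impute missing data", and that "this imputation step might be preceded by one MI approach based on MCMC method, in case of arbitrary missing pattern". It describes the covariates twice. The first description has age, gender and the components of the main model, with a pointer to a section 2.2 that is not in the SAP contents. The second has age and gender, "taking into account the baseline score of the primary endpoint", and does not list treatment.

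The jump-to-reference (J2R) step, used for the missing-not-at-random analysis, is explicit about its distribution: "The joint distribution is a Multivariate Normal model with mean parameters from the randomised arm until date of interruption (Di"). Within that J2R text, beside the description of the macro, stands the rule "In case of imputed data outside the range, the minimun or the maximun bound will be used".

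For WRC itself, SAP 4.5.3.2.3 states "A negative Binomial Regression will be used according to the general model", in type 1 patients, with MAR, J2R and observed-case results. On missing data it only refers back to 4.1.4.1. SAP 4.1.5.5 defines WRC as a weekly rate rounded to an integer. SAP 4.1.3.2 places WRC fourth of five in the fixed sequence, ahead of MWT.

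**The concern.** The SAP recognises that WRC needs a count model for analysis but does not carry this into imputation. If the regression method is the usual normal linear one, it draws from a symmetric distribution with one residual SD. For a skewed rate near zero many draws are negative, and none is naturally an integer. If negative draws are raised to 0, the mean of the imputed values rises, and by proportionally more where the expected rate is lower. If they are not raised, the negative binomial likelihood is undefined for them.

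The effect on the treatment comparison has two parts. Within the imputed values the ratio between arms is compressed. In addition, the arm with more imputed values has its overall mean inflated more. The second part can act in either direction, including in favour of pitolisant when there is no effect. SAP 4.1.3.2 claims that the fixed sequence bounds the type 1 risk at 0.05, so a bias of this kind bears on that claim for WRC and for the MWT test behind it.

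**Working it through.** The plan gives no WRC mean, dispersion, rate ratio or power, so there is no figure of its own to reproduce. The rate ratio (RR, pitolisant over placebo) is used below as the natural scale of the model. The output listed in SAP 4.5.3.2.3 is a difference of adjusted means.

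**Inputs**
- Missing fraction: protocol 7.7.2 reports V6/V7 values for 25 of 27 randomised patients, so 1 - 25/27 = 7.4%. Some of the two may still have been in follow-up. Range used: 7.4% to 30%.
- Allocation: 1:2 (SAP 4.2). Type 1 numbers are not stated. The protocol Introduction puts cataplexy at about 80%, and 0.8 x 36 and 0.8 x 72 give about 29 + 58.
- Assumed: baseline mean 3 to 15 attacks per week, gamma-Poisson overdispersion, true RR 0.5, 0.7 or 1.0.

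**Closed form.** For a draw from N(m, s) with negatives set to 0, the mean is m*Phi(m/s) + s*phi(m/s). Take placebo mean 1, RR 0.5 and s = 1 (SD equal to the placebo mean):
- placebo: 0.8413 + 0.2420 = 1.083, with 16% of draws negative
- pitolisant: 0.5 x 0.6915 + 0.3521 = 0.698, with 31% negative
- ratio among imputed values: 0.698/1.083 = 0.644 instead of 0.5
- all patients, 15% missing in each arm: (0.85 x 0.5 + 0.15 x 0.698)/(0.85 + 0.15 x 1.083) = 0.523. At 7.4% it is 0.511 and at 30% it is 0.546.

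With no effect (both means 1), 20% missing on placebo and 5% on pitolisant: (0.95 + 0.05 x 1.083)/(0.80 + 0.20 x 1.083) = 1.004/1.017 = 0.988. The direction now favours pitolisant.

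**Simulation** (60,000 to 80,000 patients, to isolate bias). Imputation was by normal regression on treatment, baseline WRC, age and sex, clipped at 0. Analysis was by negative binomial regression on treatment and baseline, with centre omitted. Between 11% and 31% of draws were negative.

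Equal missingness in both arms, true RR 0.5 or 0.7, shift in RR from full data:
- 7.4% missing: -0.002 to +0.022
- 15% missing: -0.007 to +0.045
- 30% missing: -0.007 to +0.106

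The nil or slightly negative shifts come from low dispersion (for example 0.708 to 0.701 at 30%).

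Unequal missingness:

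| Baseline mean | True RR | Missing, placebo/pitolisant | Full data | Normal, clipped | Negative binomial imputation |
|---|---|---|---|---|---|
| 3 | 1.0 | 20%/5% | 1.007 | 0.924 | 1.009 |
| 5 | 1.0 | 20%/5% | 0.999 | 0.956 | 1.003 |
| 10 | 1.0 | 20%/5% | 1.006 | 0.951 | 1.009 |
| 15 | 1.0 | 20%/5% | 1.003 | 0.979 | 1.005 |
| 10 | 0.7 | 20%/5% | 0.713 | 0.677 | 0.712 |
| 3 | 0.7 | 5%/20% | 0.726 | 0.797 | 0.726 |

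**At trial size** (29 + 58, RR 0.5, equal missingness): 0.518 to 0.518 at 7.4%, 0.533 to 0.545 at 15% and 0.508 to 0.546 at 30%. The SD of the log RR is about 0.2.

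**Variants**
- Negative draws dropped instead of clipped, 30% missing: 0.524 to 0.576, against 0.550 clipped.
- Treatment left out of the imputation model, 30% missing: 0.524 to 0.656.
- J2R at 15% missing: a negative binomial J2R moves 0.520 to 0.593, which is the intended loss of effect. The normal clipped J2R moves it to 0.620, so about 0.027 is artefact.

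**Check of the remedy.** Negative binomial imputation stayed within about 0.004 of the full-data RR in these runs. Predictive mean matching was tested in a separate simulation under one scenario: 29 + 57 children, mean 8, dispersion 1, RR 0.5, missing completely at random, 450 trials per level, log baseline as covariate. The change in log RR was 0.006 at 10% missing and -0.003 at 20%. For normal clipped imputation it was 0.040 (SE 0.006) and 0.077 (SE 0.008).

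**The case against.** The strongest reply is textual. The SAP never says normal for the MAR step, and the rule on bounds sits inside the J2R text. That is correct: normality and clipping are stated for J2R and only inferred for MAR. The inference is reasonable, since 4.1.4.1 names only the generic regression and MCMC methods and the general model in 4.1.3.1 is Gaussian. The gap does not rescue the plan, because without the bound the negative draws have no place in the negative binomial model.

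The second reply is size. At 7.4% missing the shift is at most about 0.02 on the RR, small beside an SD of about 0.2 on the log scale. This stands for similar dropout in both arms. It does not cover unequal dropout: ln(0.924/1.007) = -0.086, about 0.4 of that SD, although the SD comes from a different set of assumptions.

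The third reply is that an observed-case WRC analysis is already planned and would expose a discrepancy. It would help interpretation, but the test in the sequence is the imputed one.

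A reader might infer that the method always pulls the RR towards 1 and is therefore merely conservative. The calculations do not support that: the shift vanishes at low dispersion and reverses when placebo has more missing data.

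A reader might also extend the point to MWT, whose censoring the SAP describes as "resulting into a truncated asymmetric distribution". The documents do not carry it that far. SAP 4.1.5.5 caps observed latencies at 30 minutes, so a cap on imputed values matches the scale, and 4.5.3.2.4 has its own rule for early terminators. No MWT calculation was made, and no claim is made here.

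**Conclusion.** The mismatch is real and should be corrected. A skewed count rate goes through an imputation model that is generic for MAR and explicitly normal for J2R, and the handling of negative draws under MAR is not clearly specified. The bias is modest, and its direction cannot be known in advance. With similar missingness it is usually towards no effect (at most about 0.02 on the RR at 7.4%, up to about 0.05 at 15%), and about nil at low dispersion. With 20% missing on placebo and 5% on pitolisant it was 0.02 to 0.08 in favour of pitolisant with no true effect. That last case makes the point worth acting on for an alpha-controlled test.

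Every size rests on assumed WRC means, dispersions and missing patterns, and on reading the regression method as normal. The documents support neither a general statement that the RR is attenuated nor a finding on MWT.

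**What to change.** In SAP 4.1.4.1, keep the normal regression method for UNS, PDSS and UNS-CTP. For WRC under MAR, specify either predictive mean matching (the monotone REGPMM option in PROC MI) or a negative binomial imputation model. Name its predictors: randomised treatment, baseline WRC, age and gender. Replace the two differing covariate descriptions with one that gives treatment and each endpoint's own baseline, and correct the pointer to section 2.2. Say whether the rule on bounds applies to the MAR step as well as to J2R, and that imputed WRC values are non-negative integers.

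For J2R, state how WRC is handled: a count version of the reference-based imputation, or the existing macro on a transformed WRC with back-transformation.

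The MAR change costs one paragraph and a change to the imputation code (one option for predictive mean matching). The J2R change needs some extra programming and testing, because the cited macro is to be used with a multivariate normal model; this is the only real downside.

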#### Previous and concomitant treatments dates

Substitution rules for previous and concomitant treatments intake dates

Date to substitute		Substituted date			
	/mmm/yyyy	01/mmm/yyyy			
	//уууу	01/JAN/yyyy			
	//	If stop date is non-missing and inferior to informed consent date			
Start date		then:			
		Stop date			
		Else:			
-		Informed consent date			
	/mmm/yyyy	If patient died same month and year then			
		Date of death			
		Else			
		Last day of the month/mmm/yyyy			
	//уууу	If patient died same year then			
		Date of death			
Stop date		Else			
2004C		31/DEC/уууу			
	//	If patient died then			
		Date of death			
		Else			
		No substitution			
		( i.e. , treatment considered as still on-going)			

Note: ../mm/yyyy = missing day

../.../ yyyy = missing day and month ../.../.... = missing date

#### Substitution rules for diagnosis dates

Date to substitute		Substituted date
	/mmm/yyyy	01/mmm/yyyy
Date	//yyyy	01/JAN/yyyy
	//	No substitution

# 4.1.5 Derived variables

## 4.1.5.1 General definitions

The following definitions will be considered:

- Analysable value will be defined as any non-missing value.
- Baseline value will be defined as :
  - For UNS, PDSS and CASS parameters as the mean of V1 and V2 values on condition that values are prior to the first IMP intake (*i.e.* before or the same date as the first IMP intake date). In case of a visit missing value, the baseline will be equal to the non-missing value.
  - For other parameters, the last analysable value prior to the first IMP intake (*i.e.* before or the same date as the first IMP intake date).

Note: In case of patient randomised but not treated over the blind period: value at baseline is defined as the last analysable value prior or equal to the date of randomisation.

- Post-baseline value will be defined as any value recorded at a given timepoint after baseline.
- Change from baseline will be defined as the arithmetic difference between a post-baseline value and the baseline value for a given variable at a given time point.
- End value will be defined only for UNS, PDSS and CASS parameters as :

- The mean of V6 and V7 values. In case of a visit missing value, the End value will be equal to the non-missing value.

## 4.1.5.2 First and last IMP intake dates

For patients having taken at least one dose of IMP over the period V2-V7, the dates of first and last IMP intake on the analysis period will be defined as follows:

- The date of the first IMP intake at the first visit performed within the analysis period,
- The date of the last IMP intake at the last visit performed within the analysis period.

After selection of the dates of first and last IMP intake as defined above, if these dates are missing or incomplete, substitution rules will be applied to identify baseline value and emergent adverse events.

# 4.1.5.3 Completers

- Completers the double blind period Patients who completed the study until the visit V7.
- Completers the blind period Patients who completed the study until the visit V8.

## 4.1.5.4 Baseline characteristics

Previous treatments

**The existence of a previous treatment** (Yes/No) is defined from the presence, or not, of an Anatomical therapeutic chemical classification and/or Preferred name.

**Previous treatment** is defined as any treatment with associated stop date strictly inferior to the first IMP intake date.

Note: In case of patient randomised but not treated the previous treatment is defined as any treatment with an associated stop date strictly inferior to the date of the randomisation visit.

## Concomitant treatment

**The existence of a concomitant treatment** (Yes/No) is defined from the presence, or not, of an Anatomical therapeutic chemical classification and/or Preferred name.

The periods considered for the analysis are:

- At inclusion for which treatments with start date ≤ inclusion date (V2) and stop date ≥ inclusion date (V2) or missing are taken into account.
- **During the treatment period** for V2-V7 period for which treatments:
  - with start date ≥ first IMP intake date and < last IMP intake date, or
  - with start date ≤ first IMP intake date and stop date ≥ first IMP intake date or missing date are taken into account.

Concomitant treatments could be considered in one or several of the possible analysis periods.

**Intake of oxybate sodium** (Yes/No): A patient will be considered to have taken at inclusion or during the treatment period a concomitant treatment which the Standardized Medication Name="OXYBATE SODIUM".

- Narcolepsy duration (years) (Inclusion visit date (V2) - confirmed diagnosis date +1) /365.25
- Study duration (in days)
   Last visit date until V8– Inclusion visit date (V2) + 1
- Treatment duration (in days) on V2-V7 period

Last IMP intake date - First IMP intake date + 1

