3.6.1. Authorized concomitant treatments

Double-blind period:

If Patients are treated with sodium oxybate, a stable dosage is required for a minimum period of 4 weeks prior to inclusion (V2), and this dosage should be maintained stable

throughout the study.

Other purported anticataplectic treatments e.g. SSRI (fluoxetine, fluoxamine, citalopram,

sertraline, paroxetine) or norepinephrine/serotoninergic uptake inhibitor (venlafaxine),

norepinephrine uptake inhibitors (viloxazine, duloxetine, reboxetine, atomoxetine) are

authorized only if they are maintained at stable dose for a minimum period of 4 weeks prior

to inclusion (V2), and their dose should not be changed throughout the trial.

Antihistamic H1 which do not cross blood brain barrier (BBB) (2nd and 3rd generation).

Any change in the dosage of the other authorized concomitant treatments should be

recorded in the CRF.

Open label period:

Concomitant treatments against EDS and cataplexy such as modafinil, sodium oxybate, methylphenidate or antidepressants (except tricyclics) are authorized. The investigator will be

free to adapt posology.

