## 4.5.3.1.2 Sensitivity and other analyses

Sensitivity analyses will be performed to assess the robustness of the primary analysis results:

- Using MNAR option of the MI imputation (removing the treatment effect in the imputation model of the partially-complete data sets).
- Using the same model as for the primary analysis will be performed with the center as fixed effect instead of random effect.
- Using the same model as for the primary analysis will be performed with in addition the oxybate sodium intake and treatment-by- oxybate sodium intake interaction as fixed effects.
- Using an observed Cases analysis: The same model as for the primary analysis will be performed in patients having a value of UNS total score at V6 or V7 (i.e. in this case analysis restricted to completers the double blind period).
- Using the same model as for the primary analysis will be performed by actual treatment group, only if actual group is different from randomized group.

The same statistical elements to estimate the treatment effect as for primary analysis will be provided.

In addition, value and change from baseline descriptive statistics at each visit by treatment group will be provided, overall and by subgroups.

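### The sodium oxybate factor in the sensitivity model can be changed by intake after randomisation; it should be fixed at V2 (low severity, sensitivity analysis only)

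*SAP*

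**What the plan says.** SAP 4.1.5.4, headed as baseline characteristics, defines two periods for concomitant treatments. The first is fixed before treatment: "At inclusion for which treatments with start date ≤ inclusion date (V2) and stop date ≥ inclusion date (V2) or missing". The second covers the V2-V7 treatment period and admits new treatments: "with start date ≥ first IMP intake date and < last IMP intake date, or". The oxybate variable then joins the two: "A patient will be considered to have taken at inclusion or during the treatment period a concomitant treatment", identified by the standardised medication name.

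SAP 4.5.3.1.2 lists five sensitivity analyses. Their purpose: "Sensitivity analyses will be performed to assess the robustness of the primary analysis results". One refits the primary model "with in addition the oxybate sodium intake and treatment-by- oxybate sodium intake interaction as fixed effects". It does not say which period applies, and 4.1.5.4 holds the only definition. Sections 4.5.3.2.1 (PDSS) and 4.5.3.2.2 (UNS-CTP, type 1 patients) repeat the primary analysis with its sensitivity analyses. The primary model in 4.1.3.1 contains baseline, treatment and centre, and no oxybate term.

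Protocol 3.6.1 sets the condition for oxybate in the double-blind period: "If Patients are treated with sodium oxybate, a stable dosage is required for a minimum period of 4 weeks prior to inclusion (V2"). Protocol 3.4 adds that anticataplectic doses stay stable from V2 to V8. A first intake after V2 is therefore a departure from the protocol.

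**The concern.** A factor used for adjustment and interaction should be settled before randomisation. Here a child can move from No to Yes afterwards. The protocol's introduction describes oxybate as a treatment for cataplexy attacks. Cataplexy supplies four of the eleven UNS items and all of UNS-CTP. A start after V2 could therefore be a reaction to the symptom being scored, and treatment can influence that symptom.

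Suppose such starts are more frequent on placebo. Poorly controlled placebo children then leave the non-user stratum, which shrinks the apparent effect there. They join the stable background users, which inflates it there. An analysis meant to show that the result is robust to background oxybate could then suggest heterogeneity that does not exist.

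**Working it through.** The documents give no figure for oxybate use or post-V2 starts, so there is no stated result to reproduce. The calculation is illustrative.

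**Inputs from the documents.** 36 placebo + 72 pitolisant, R = 0.4, two-sided 0.05 (SAP 4.2). A difference of 3 UNS points (protocol synopsis) with a standardised difference of 0.5 (SAP 4.2) implies SD = 3/0.5 = 6.

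**Assumptions.** True effect -3 in every child; background use 15%, 25% or 30%; starter counts as shown; no effect of oxybate itself unless stated; centre term omitted.

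**Model.** Final UNS = a + b·baseline + c·treatment + d·oxybate + e·(treatment × oxybate). The effect is c in non-users and c + e in users. It is fitted once with the SAP factor and once with oxybate ongoing at V2.

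**Run 1: scores kept after a start.** 1,500 trials per row. Starters are the non-users in each arm with the highest final UNS plus random noise (a sharp selection). Two averages follow by arithmetic: equal weights, (c + (c + e))/2; and weights by observed share of users, p = background use + starters/108.

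| Users at V2 | Starters, placebo/pitolisant | Non-users | Users | Equal weights | Share weights |
|---|---|---|---|---|---|
| 15% | 1/0 | -2.74 | -4.56 | -3.65 | -3.03 |
| 15% | 2/2 | -2.73 | -3.89 | -3.31 | -2.95 |
| 15% | 2/0 | -2.39 | -5.61 | -4.00 | -2.93 |
| 15% | 4/2 | -2.29 | -4.72 | -3.51 | -2.79 |
| 15% | 4/4 | -2.51 | -3.78 | -3.15 | -2.79 |
| 30% | 1/0 | -2.57 | -3.96 | -3.27 | -3.00 |
| 30% | 2/2 | -2.71 | -3.42 | -3.07 | -2.95 |
| 30% | 2/0 | -2.25 | -4.32 | -3.29 | -2.91 |
| 30% | 4/2 | -2.12 | -4.01 | -3.07 | -2.79 |
| 30% | 4/4 | -2.40 | -3.56 | -2.98 | -2.83 |

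Example of the last column, row 1: p = 0.15 + 1/108 = 0.159; 0.841 × (-2.74) + 0.159 × (-4.56) = -3.03.

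With the V2 factor every scenario returns -2.9 to -3.15 in both strata. With no starters the two factors are identical. With starters chosen at random, the SAP factor returns -2.95 to -3.04 in non-users and -2.92 to -3.08 in users.

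**Run 2: 25% users, scores kept, starters from the worst third of non-users.** With 3/2 starters (8% and 3% of the arms) the SAP factor gives -2.5 and -3.9. With 4/2 it gives -2.2 and -4.2. With 6/2 it gives -1.6 and -4.7, and the interaction is significant in 22% to 24% of trials. A further run at 6/2 gave -2.0 and -4.2 with 15%. The V2 factor gives about -3.0 in both strata, with 5% to 6% rejection.

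**Run 3: 25% users, scores after a start removed and imputed from arm and baseline.**

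| Starters | SAP factor, non-users/users | V2 factor, non-users/users | Interaction rejected, SAP/V2 |
|---|---|---|---|
| 3/2 | -2.7 / -3.0 | -2.7 / -3.0 | 5% / 5% |
| 4/2 | -2.5 / -2.8 | -2.5 / -2.9 | 5% / 5% |
| 6/2 | -1.95 / -2.75 | -2.05 / -3.1 | 6% / 7% |

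The inflated user effect and the false interaction are gone. The attenuation in non-users comes from discarding the worst placebo scores and is nearly the same under both definitions.

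**The case against.** **The bias is conditional.** It needs starts that the protocol does not allow, and those starts must depend on response. A reader might infer that the factor does distort the effect. The documents support only that it can. This stands.

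**The affected figures are not listed outputs.** SAP 4.5.3.1.2 promises the same elements as the primary analysis: an adjusted difference, its interval and a p-value. Stratum effects and the interaction test are not named, and the stratum biases partly cancel. This stands in the main. Weighted by observed share, the difference stays between -2.8 and -3.0 in Run 1. With equal weights it stays near -3 at 25% to 30% use, but at 15% use with starters only on placebo it reaches -3.65 to -4.00. The SAP does not say which weights apply.

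**Such scores may never enter.** The estimand table (4.5.3.1.1) uses data only up to a prohibited medication, and 4.1.4.1 speaks of censoring after a deviation, with MAR imputation. UNS is scheduled only at V1, V2, V6 and V7, so a start before V6 would leave nothing on treatment to keep. Under that handling Run 3 applies and most of the problem vanishes. It does not settle the matter: the table does not name oxybate, and protocol 3.6.2 does not list it as prohibited.

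**If oxybate works, the V2 factor also misses -3.** With an assumed 3-point benefit in starters, the SAP factor gives -3.0 to -3.2 in users, and the V2 factor gives -2.4 to -2.75 in non-users. The latter is a change of quantity, not a fault of the factor. With 27 placebo and 54 pitolisant non-users, 6/2 starters shift the true contrast by 3 × 6/27 - 3 × 2/54 = 0.56, to -2.44.

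**Other safeguards.** Non-allowed medication is reviewed before database lock (4.4). Efficacy is repeated in the per-protocol set when that set is below 90% of the FAS (4.3). These help, but leave the factor undefined for the model.

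**Two flags may be meant**, one per period. Then 4.5.3.1.2 does not say which enters, and the same clarification is needed.

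**Conclusion.** The point holds as a defect of definition with a conditional consequence. As written, the sensitivity model can condition on an event after randomisation. The size depends wholly on assumed use, starter counts and how strongly starts follow poor response. With scores kept, a few response-driven starters, relatively more frequent on placebo, move a true -3 to about -1.6 to -2.8 in non-users and -3.4 to -5.6 in users. Interaction rejection is close to nominal with few starters (6% at 3/2, 8% at 4/2) and reaches 15% to 24% only at 6/2, where 17% of placebo children have started. With no starters, or starts unrelated to response, nothing changes.

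Two stronger readings are not supported. The primary result and the fixed-sequence tests are unaffected, because neither uses the factor. And a V2 factor does not guarantee -3 in both strata: if scores are censored and imputed, non-users are attenuated under either definition. Severity is low: a free improvement to a sensitivity analysis.

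**What to change.** In SAP 4.1.5.4, define the model factor as sodium oxybate ongoing at V2, using the inclusion window already there. Refer to it by that name in 4.5.3.1.2, so that it carries over to PDSS and UNS-CTP. Keep intake during V2-V7 for the descriptive tables only. Add a sentence that a first intake after V2 is reported as a protocol deviation and handled as an intercurrent event under the estimand table in 4.5.3.1.1, so that it is clear whether later scores are used.

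The cost is one or two sentences and one line of derivation code, with no new data. If nobody starts oxybate after V2, the results are unchanged. The edit should be made before unblinding.
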